2. LAY SUMMARY

Patient over 70 are very commonly admitted to hospital with problems caused by gallstones, such as pain, infection, jaundice and pancreatitis (inflammation of the pancreas, a digestive organ which can get blocked by gallstones). Some people have their gallbladder removed during their initial admission and others are treated first with medical therapy (such as antibiotics or an endoscopy) then brought back later to have their gallbladder removed as a planned (or "elective") operative. This usually prevents further problems caused by gallstones. A third group of patients may not be offered surgery at all, usually because they are elderly, frail or have other medical problems which make surgery more risky. Very little is known about what happens to these patients – such as whether the gallstones do cause more problems and how this affects their quality of life. This study aims to follow up patients who were admitted to hospital with gallstone disease to assess how this has affected them for up to three years after their initial diagnosis and compare those who did and those who didn't have surgery. Patients will be contacted regularly to ask whether they have any ongoing symptoms and how this affects their quality of life. This is an observational study which will not affect which treatment each patient receives - this will be decided as normal by the team treating them in hospital. A better understanding of what happens to patients after surgical and nonsurgical treatment would allow doctors to have more informed discussions with patients about the likely outcomes of each treatment and improve their ability to make a joint decision about whether surgery is the best option.

3. SYNOPSIS

Trial Title	Managing Gallstone Disease in the Elderly: Comparing Quality of Life and
	Outcomes after Operative and Non-Operative Treatment

IRAS ID: 301556

Internal ref. no. (or short title)	MANGO		
Trial registration	To be registered on clinicaltrials.gov		
Sponsor	Portsmouth Hospitals Unive	ersity NHS Trust	
	Queen Alexandra Hospital	, [name]
Funder	Rosetrees Trust		
Clinical Phase	Observational		
Trial Design	Observational		
Trial Participants	All patients aged 70 and ove	er admitted acutely with gallst	one disease
Sample Size	290 (assuming readmission rate of 5% vs 30% with alpha of 0.05 and power of 0.9)		
Planned Trial Period	Recruitment period of 1 year with follow up of 3 years (study period 4 years in total)		
Planned Recruitment period	April 2022 – March 2023		
	Objectives	Outcome Measures	Timepoint(s)
Primary	Compare gallstone- related readmission rates among operative and non- operative groups	Number of patients readmitted with gallstone-related problems	30 days, 1 year, 3 years
Secondary	Morbidity Mortality Quality of Life	Number of patients with complications Number of patients who have died Gastrointestinal Quality of Life Index (GIQLI)	30 days, 1 year, 3 years
Intervention(s)			
• IMP(s)			
• nIMP(s)	None		

IRAS ID: 301556

Other intervention(s)	
Comparator	N/A
'	'

4. ABBREVIATIONS

AE	
712	Adverse event
AR A	Adverse reaction
CI C	Chief Investigator
CRA C	Clinical Research Associate (Monitor)
CRF C	Case Report Form
CRO C	Contract Research Organisation
СТ С	Clinical Trials
СТА С	Clinical Trials Authorisation
CTRG C	Clinical Trials and Research Governance
DMC/DMSC D	Data Monitoring Committee / Data Monitoring and Safety Committee
DSUR D	Development Safety Update Report
GCP G	Good Clinical Practice
GP G	General Practitioner
GTAC G	Gene Therapy Advisory Committee
HRA F	Health Research Authority
IB II	nvestigators Brochure
ICF II	nformed Consent Form
ICH II	nternational Conference on Harmonisation
IMP II	nvestigational Medicinal Product
IRB II	ndependent Review Board
MHRA N	Medicines and Healthcare products Regulatory Agency
NHS N	National Health Service
RES I	Research Ethics Service
PI P	Principal Investigator

IRAS ID: 301556

PIL	Participant/ Patient Information Leaflet
R&D	NHS Trust R&D Department
REC	Research Ethics Committee
RSI	Reference Safety Information
SAE	Serious Adverse Event
SAR	Serious Adverse Reaction
SDV	Source Data Verification
SMPC	Summary of Medicinal Product Characteristics
SOP	Standard Operating Procedure
SUSAR	Suspected Unexpected Serious Adverse Reactions
TMF	Trial Master File

5. BACKGROUND AND RATIONALE

Gallstone disease is the most common surgical cause of hospital admission in developed countries¹ and the most common indication for abdominal surgery²³. The prevalence increases progressively with age ^{1,2,4}. The incidence of gallstones in those aged 80 or over is as high as 38-53%^{5,6}, and has been reported to be as high as 80% for patients over 90 years of age⁷. Older patients are known to be at greater risk of complications of gallstones than younger patients, and are more likely to present with cholecystitis, choledocholithiasis and pancreatitis⁸, as opposed to uncomplicated biliary colic. While modern guidelines^{9,10} advise surgical management of gallstone disease in the typical patient, it is unclear whether these should also apply to the elderly, who often have pre-existing conditions and diminished physiological reserve which may affect their suitability for surgery.

Currently, published reports suggest that older patients are less likely to be managed surgically, with up to 30% of older patients managed non-operatively^{11–13}. In cases where intervention is required, ERCP for ductal stones or cholecystostomy are considered. However, up to a third of patients may have recurrent problems when managed non-operatively¹⁴. Long term follow-up in these patients is lacking and there is

IRAS ID: 301556

no real data comparing mid- to long-term outcomes, readmission rates or quality of life in patients undergoing these procedures compared with the definitive management of cholecystectomy.

This study aims to investigate the differences in outcomes, readmission rates and quality of life when comparing older patients (defined as at least 70 years of age) who are admitted with acute biliary disease (including biliary colic, cholecystitis, choledocholithiasis and pancreatitis) and are treated operatively compared with those who are managed with medical treatment only.

6. OBJECTIVES AND OUTCOME MEASURES

Objectives	Outcome Measures	Timepoint(s) of evaluation of this outcome measure (if applicable)
Primary Objective To compare the rate of gallstone- related hospital re-admission between patients treated operatively and non-operatively	Number and percentage of patients readmitted to hospital with gallstone-related disease by each timepoint.	30 days, 1 year, 3 years
1. To compare morbidity in operative and non-operative groups 2. To compare mortality in operative and non-operative groups 3. To compare quality of life in operative and non-operative groups	Number and percentage of patients with complications in each group Number and percentage of patients who have died in each group Gastrointestinal Quality of Life Index (GIQLI) in each group	30 days, 1 year, 3 years
Exploratory Objectives To assess the result of frailty on		

IRAS ID: 301556

morbidity, mortality and quality of	Morbidity, mortality and quality of life	30 days, 1 year, 3	l
life (as defined above)	according to Rockwood frailty score	years	l
To assess whether frailty affects	Comparison of Rockwood frailty score in		
whether or not surgery is carried	operative and non-operative groups both		
out	before and after surgery.		l
	- ,		

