9.7. Subsequent Visits

Patients will be contacted by telephone at 30 days, 1 year and 3 years from registration. Prior to any contact, the hospital EPR and CHiE will be checked to ensure that the patient is still alive.

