11.5. Reporting Procedures for Serious Adverse Events

Serious adverse events will not be reported as this is an observational trial.

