12.2. Description of Statistical Methods

Continuous data will be summarized using descriptive statistics (mean, median, standard deviation, quartiles, minimum and maximum) and categorical data will be summarized using counts and

IRAS ID: 301556

percentages. The proportion of patients undergoing operative compared to non-operative treatment will be reported.

Primary endpoint

The primary endpoint will be reported as the percentage of patients re-admitted with gallstone related problems after operative vs non-operative management during their index admission.

Secondary endpoints

Data will be reported at 30 days, 1 year and 3 years. Patients who have had complications or have died in each group will be reported as a number and percentage. Comparison between groups will be carried out using Chi squared test. Gastrointestinal Quality of Life Index (GIQLI) in each group will be reported as a median and range. Paired T test will be used to compare groups.

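### The mortality comparison is an unadjusted test of all-cause deaths between groups selected partly on frailty, with no outcome that isolates gallstone-related or operation-related deaths

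*Protocol*

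**What the plan says.** Section 6 lists as a secondary objective "To compare mortality in operative and non-operative groups". The outcome measure is "Number and percentage of patients who have died in each group", at 30 days, 1 year and 3 years.

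Section 12.2 repeats the three timepoints ("Data will be reported at 30 days, 1 year and 3 years") and the summary ("Patients who have had complications or have died in each group will be reported as a number and percentage"). The test follows: "Comparison between groups will be carried out using Chi squared test". No covariate or stratum is named.

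The other places that bear on this are:

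- **Selection (section 2, lay summary; section 9.4).** Treatment is not randomised. Patients not offered surgery are described as usually older, frail or with other illness that raises surgical risk.
- **Frailty (sections 6 and 9.6).** Frailty is assessed at baseline. Mortality by Rockwood score, and a comparison of the score between the groups, are exploratory objectives.
- **Source of vital status (section 9.7).** Before each contact "the hospital EPR and CHiE will be checked to ensure that the patient is still alive". Section 7 adds that hospital and GP records may be used for follow-up.
- **Adverse events (section 11.5).** "Serious adverse events will not be reported as this is an observational trial".
- **Plan (section 12.1).** No separate SAP is in use, so section 12 is the whole analysis plan.

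**The concern.** The objective calls for a comparison of deaths between two groups that the protocol itself describes as differing in age, frailty and comorbidity. Those factors drive death over three years in people aged 70 and over, whatever is done about gallstones. An unadjusted test cannot tell that difference in case mix from an effect of operating or not operating.

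The deaths that bear on the treatment choice are those from recurrent gallstone disease and those from an operation. The protocol restricts its primary endpoint to gallstone-related readmission but has no corresponding restriction or breakdown for death.

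The lay summary says the results should inform discussions with patients about the likely outcome of each treatment. A significant crude gap in mortality could be taken in those discussions as harm from not operating. Equally, a real excess of operative or gallstone deaths in one group could go unnoticed among the other deaths.

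**Working it through.** **1. Is the comparison adjusted, or cause of death specified, anywhere?**

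- Section 12.2 gives the chi-squared test alone.
- The Rockwood objective in section 6 tabulates mortality by frailty. It does not compare operative with non-operative patients within frailty levels.
- No section defines a gallstone-related or operation-related death. Section 9.7 describes a check on whether the patient is alive, and section 11.5 closes the serious adverse event route.
- Section 12.1 rules out a separate SAP that could supply either.

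**2. Group sizes.** Section 12.3 gives 260 evaluable patients and a 1:9 ratio: 260 × 0.1 = 26 non-operative and 260 × 0.9 = 234 operative.

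**3. How often would the planned test be significant from selection alone?** The protocol states no mortality rate, so there is no figure of its own to reproduce and all rates here are assumptions. Management is taken to have no effect on death; the two rates differ only because of who is in each group.

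For x deaths among n₁ = 26 and y among n₂ = 234, with N = 260, the uncorrected statistic is

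X² = N [x(n₂ − y) − y(n₁ − x)]² / [n₁ n₂ (x + y)(N − x − y)],

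significant at two-sided 0.05 if X² ≥ 3.84. The exact probability is the sum of Bin(x; 26, p₁) × Bin(y; 234, p₂) over all significant pairs.

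| Assumed 3-year mortality, non-operative v operative | Expected deaths (26p₁ v 234p₂) | P(significant) |
|---|---|---|
| 20% v 12% | 5.2 v 28.1 | 0.24 |
| 25% v 12% | 6.5 v 28.1 | 0.45 |
| 30% v 12% | 7.8 v 28.1 | 0.66 |
| 40% v 15% | 10.4 v 35.1 | 0.84 |
| 12% v 12% (no selection) | 3.1 v 28.1 | 0.045 |

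The last row shows that the test keeps its nominal level when there is no selection.

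**4. Sensitivity to how the rates arise.** Suppose mortality depends only on frailty, at 30% to 50% if frail and 10% to 15% if not, and 60% to 80% of the non-operative group are frail against 20% to 30% of the operative group (all assumed).

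- Mildest: non-operative 0.6 × 0.30 + 0.4 × 0.15 = 24.0%; operative 0.3 × 0.30 + 0.7 × 0.15 = 19.5%; gap 4.5 points; P(significant) about 0.09.
- Strongest: non-operative 0.8 × 0.50 + 0.2 × 0.10 = 42%; operative 0.2 × 0.50 + 0.8 × 0.10 = 18%; gap 24 points; P(significant) about 0.78.

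These two probabilities use the normal approximation at 26 v 234.

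**5. If more patients are managed without surgery.** Section 5 cites up to 30% managed non-operatively. At 78 v 182 the four selection scenarios in step 3 give 0.40, 0.73, 0.93 and 0.99.

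**The case against.** All-cause death is an objective and legitimate endpoint, and the protocol never claims that it measures gallstone deaths. That stands; the recommendation keeps it.

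A reader might infer that mortality is just one 3-year count that reflects who was chosen for surgery and nothing else. The documents do not support that. Deaths are also reported at 30 days and 1 year, and the count includes gallstone and operative deaths; it only fails to separate them. The 30-day figure says something about early deaths. However, contacts are timed "Patients will be contacted by telephone at 30 days, 1 year and 3 years from registration", and section 12.4 counts surgery after the index admission as operative, so for those patients the figure is not post-operative mortality.

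A reader might also infer that date and cause of death will not be collected. That goes beyond the text. The case report form is not shown, section 7 allows use of hospital and GP records, and the section 9.7 check is made before contacting patients rather than as a definition of the mortality data. The supportable statement is that no cause-specific outcome is specified.

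Frailty is not ignored: the exploratory objectives let readers see the selection. They do not remove it from the group comparison.

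The strongest objection is that the probabilities above measure confounding, so adding a cause of death would leave them unchanged. This is right. Cause fields help interpretation; only adjustment or stratification addresses the selection on measured factors. Finally, with about 26 non-operative patients, cause-specific deaths will be few and attributed by staff who know the treatment. That argues for describing them without a test.

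**Conclusion.** The point holds. As planned, the mortality comparison cannot be read as an effect of operating or not operating, and the plan offers no way to pick out the deaths relevant to treatment.

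Under assumed 3-year mortality of 20% to 40% against 12% to 15%, with no effect of management, the test would be significant in about 24% to 84% of studies at 26 v 234, where about 5% would be expected without selection. With milder assumed selection the figure falls to about 9%. Whether a false signal is likely therefore depends on rates that the protocol does not give. That the crude test confounds selection with management does not depend on them; it follows from the protocol's own account of who is not offered surgery.

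This concerns a secondary outcome and should be corrected. It does not bear on the sample size, which was set for readmission.

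**What to change.** In sections 6 and 12.2:

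1. Keep all-cause mortality at 30 days, 1 year and 3 years, reported as counts and percentages.
2. Compare the groups with adjustment for, or stratification by, baseline Rockwood score and age. Keep the model sparse, for example treatment, Rockwood score and age as three terms. The step 3 selection scenarios imply about 33 deaths (5.2 + 28.1) to 46 deaths (10.4 + 35.1) by 3 years, with only 5 to 10 of them in the non-operative group.
3. Record the date and recorded cause of each death from hospital or GP records. Report gallstone-related, operation-related, other and not-determinable deaths by group at each timepoint, descriptively and without a significance test.
4. State that the crude all-cause difference is not interpreted as an effect of management.

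**Cost.** Two fields on the case report form for patients who die, from records the sites already consult, and one small model on baseline data already planned. Attribution of cause will sometimes be uncertain and is made by staff who know the treatment; cause-specific counts will be small; and adjustment for two factors will not remove all selection, notably that due to comorbidity.

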9.6. Baseline Assessments

Demographic data will be collected from the participant's medical records. Frailty will also be assessed at baseline

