12. STATISTICS

12.1. Statistical Analysis Plan (SAP)

The plan for the statistical analysis of the trial are outlined below. There is not a separate SAP document in use for the trial.

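### The exploratory question of whether frailty affects the decision to operate is to be answered by an unadjusted comparison of Rockwood scores, partly taken after surgery, which cannot separate frailty from age

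*Protocol*

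**What the plan says.** Protocol section 6 lists two exploratory objectives. The second asks whether frailty influences the decision to operate. Its outcome measure begins "Comparison of Rockwood frailty score in", continues "operative and non-operative groups both" and ends "before and after surgery". No covariate, stratification or model is named there. Section 12.2 gives no method for the exploratory objectives, and section 12.1 states: "There is not a separate SAP document in use for the trial".

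On age, the lay summary explains that some patients are not offered surgery, "usually because they are elderly, frail or have other medical problems which make surgery more risky". Section 5 adds that "published reports suggest that older patients are less likely to be managed surgically" and describes the elderly as people "who often have pre-existing conditions and diminished physiological reserve which may affect their suitability for surgery".

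On the data, section 9.6 states: "Demographic data will be collected from the participant's medical records. Frailty will also be assessed at baseline". Age is also needed to apply the inclusion criterion in section 8.2.

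**The concern.** Two things in this measure do not fit the question.

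First, age is on the protocol's own list of reasons for not operating, alongside frailty. If older patients in this cohort also tend to be frailer, the non-operated group will have higher Rockwood scores even where clinicians looked only at age. A crude comparison would then be read as evidence on frailty.

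Second, a score taken after the operation is not a possible cause of the decision to operate. It may also reflect the operation itself. For patients who had none, the time point does not exist, so the two groups cannot be compared at it.

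At stake is the interpretation of one exploratory result. Adjusting the readmission, mortality or quality-of-life comparisons would not help, because treatment is the outcome here.

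**Working it through.** **Inputs from the protocol.** The target is 290 patients and about 10% are expected to be non-operated, a 1:9 ratio (section 12.3). Section 5 mentions up to 30% managed non-operatively. The significance level is 0.05 (section 12.7). No figure is stated for this objective. The target is consistent with section 12.3: 260 / 0.9 = 288.9, so 289, rounded up to 290. Expected non-operated patients: 0.10 × 290 = 29.

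**Assumptions, not in the protocol.** These are the correlation r between age and frailty, and the odds ratio of non-operative management per standard deviation (SD) of age.

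**Model.** Age a is standard normal. Frailty is f = r·a + √(1 − r²)·e, with e independent standard normal. The decision depends on age only: logit P(no surgery) = c + ln(OR)·a, with c set to give 10% or 30% non-operated overall. Frailty therefore has no effect of its own, and a sound analysis should be positive in about 5% of studies.

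**Crude comparison** (two-sample t test at 0.05, 1,000 simulated studies per cell), percentage positive:

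| Non-operated | r | OR 1.5 | OR 2 | OR 3 |
|---|---|---|---|---|
| 10% | 0.1 | 4.4 | 6.5 | 8.4 |
| 10% | 0.3 | 10.6 | 18.8 | 32.8 |
| 10% | 0.5 | 18.9 | 35.9 | 72.5 |
| 30% | 0.1 | 7.3 | 7.3 | 11.5 |
| 30% | 0.3 | 15.1 | 31.8 | 57.4 |
| 30% | 0.5 | 32.9 | 70.9 | 94.3 |

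At r = 0 the crude test was positive in 3.8% to 5.7%, as it should be.

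**Hand check.** With 29 and 261 patients the standard error of the mean difference, in SD units, is √(1/29 + 1/261) = 0.196. At r = 0.5 and OR 3 the mean frailty difference was 0.50 SD. Then 0.50 / 0.196 = 2.55, and Φ(2.55 − 1.96) = 0.72, against 72.5% simulated. At r = 0.3 and OR 2 the difference was 0.21 SD. Then 0.21 / 0.196 = 1.07, and Φ(1.07 − 1.96) = 0.19, against 18.8%.

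**With age in the model.** Logistic regression of the decision on frailty and age (400 studies per cell) gave a positive frailty term in 3.5% to 7.8% across the same cells. The simulation error at 5% is √(0.05 × 0.95 / 400) = 1.1 percentage points, so this is close to nominal; one cell (7.8%) is on the high side.

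**Second simulation.** This used a 1-to-9 score, a Mann-Whitney test, 10% non-operated, and an age gap between groups of 0.5, 0.75 or 1.0 SD (1,500 studies per setting). The crude comparison was positive in 11%, 20% and 28% at r = 0.3; 14%, 30% and 50% at r = 0.4; and 24%, 45% and 70% at r = 0.5. The age-adjusted model stayed at 4% to 6%.

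**Room for covariates.** With 29 non-operated patients, two terms leave 29 / 2 = 14.5 per term and three leave 29 / 3 = 9.7.

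**Timing, by text.** Section 9.6 places the frailty assessment at baseline. Section 6 asks for scores on both sides of an operation. Only the first of these can bear on the decision.

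**The case against.** The strongest reply is that the wording sits in an outcome-measure column and is not a test specification. Section 12.2 names no test for exploratory aims, the protocol does not forbid adjustment, and describing whether non-operated patients are frailer is a legitimate exploratory summary. That much stands. But the objective asks whether frailty affects the decision, this comparison is the only measure offered for it, and the protocol says no separate plan will supply another.

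A reader might infer more than the documents support:

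- **That comparing scores between treatment groups is the wrong way round.** It is not an error in itself. It tests the same null of no association as an unadjusted logistic regression of surgery on frailty. The fault is the missing adjustment.
- **That the study will report an age effect as a frailty effect.** The protocol gives neither an age-frailty correlation nor an age gap between groups, and does not state a gradient within patients already aged 70 or over. At r = 0.1 and 10% non-operated the error rate is near nominal. Deciding on age alone is also an extreme case, since the lay summary lists frailty and other illness as reasons too.
- **That the shared-decision purpose is defeated.** In the lay summary that purpose rests on what happens to patients after each treatment. It does not rest on how they were selected for it.
- **That adjusting for age isolates frailty.** The lay summary also names other medical problems. Comorbidity, diagnosis and site would remain as possible explanations.

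**Conclusion.** The point holds in a limited form. As written, the measure cannot separate frailty from age, which the protocol itself treats as a separate driver of non-operative management. Half of it also uses a score that cannot have influenced the decision and that non-operated patients cannot have.

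The size is illustrative. With surgery depending on age alone and 10% non-operated, the false-positive rate runs from 4% to 8% at an assumed correlation of 0.1 up to about 70% at 0.5 with a strong age effect. At 30% non-operated it runs from 7% to 94%. The documents do not show where in that range this cohort lies.

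The objective is exploratory and the primary and secondary endpoints are untouched, so the priority is low to moderate.

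**What to change.** In section 6, replace the measure for this objective with a logistic regression of surgery (yes/no) on the baseline Rockwood score and age in years, with at most one further term given about 29 expected non-operated patients. Report the odds ratio per Rockwood point with its 95% interval, and state that confounding by comorbidity and other factors may remain. Drop the after-surgery score from this objective. Crude scores by group can stay as description.

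Define surgery once. Section 12.2 classifies patients by their management in the index stay, whereas section 12.4 also counts operations after it. The two must be reconciled, because they give the regression different outcomes and different numbers of non-operated patients.

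The cost is protocol wording and one model on data already collected. The frailty interval widens by a factor of roughly 1/√(1 − r²), borrowing the linear-model approximation: 1/√0.99 = 1.005 at r = 0.1, 1/√0.91 = 1.05 at 0.3 and 1/√0.75 = 1.15 at 0.5.
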